6.2.2 Clinical events

AE's, including SAE's, will be coded by body system, preferred term, severity, relation to procedure, and outcome. Specifically, any noted skin erosion above the access site or complications associated with wound healing will be documented and reported.

6.3 Secondary endpoints

1. Time to primary patency cessation since the fistula creation
2. Time to assisted primary patency cessation since the creation
3. Time to primary patency cessation since the first intervention (post-intervention primary patency)
4. Time to assisted primary patency cessation since the first intervention (post -intervention assisted primary patency)
5. Time to first successful cannulation
6. Time to secondary patency cessation since the fistula creation
7. Time to secondary patency cessation since the first intervention (post intervention secondary patency)
8. Time to fistula maturation (physiological)
9. Time to 100% functional fistula dependency

Document title:
VasQ FDA pivotal Protocol

Document No.
CD0121

Revision
12.0
14 March 2021

Page
15 of 42

10. Unassisted maturation at 3 months defined as vein diameter $\geq 5\text{mm}$ and blood outflow ≥ 500 (-50) mL/min by Doppler ultrasound.
11. Primary patency at 6 months post AVF creation, excluding patients who have received balloon angioplasty procedures directed at cephalic arch and central vein stenosis.
12. Time to first intervention.
13. Number of interventions (including type and outcome)
14. Rate of interventions per patient-years
15. Primary Failure, at 6 months, which is fistula permanent failure before hemodialysis suitability.
16. Target artery / target vein flow (mL/min) at 1, 3 and 6 months by Doppler blood outflow measurement.
17. Target artery /target vein diameter at 1, 3 and 6 months by Doppler measurement.
18. Target artery / target vein PSV (Peak Systolic Velocity, cm/sec)
19. Proportion of fistulas used for hemodialysis at 3 and 6 months post AVF creation.
20. Duration between fistula first use for dialysis and final abandonment

6.4 Endpoint definitions

1. Primary patency: The time of access creation or placement until any first intervention (endovascular or surgical) to maintain or restore blood flow, or first occurrence to access thrombosis.

[REDACTED]

[REDACTED]

[REDACTED]

[REDACTED]

[REDACTED]

[REDACTED]

[REDACTED]

[REDACTED]

[REDACTED]

Proportion of patients (rate) with primary patency can be calculated at defined time points.

2. Secondary patency: the time of access creation or placement until access abandonment, and includes all surgical and endovascular interventions.
Proportion of patients (rate) with secondary patency can be calculated at defined time points.
3. Primary failure: Fistula permanent failure before hemodialysis suitability.
Proportion of patients (rate) with primary failure can be calculated at defined time points.
4. Primary assisted patency: The time of access creation or placement until any first intervention (endovascular or surgical) to restore blood flow of a thrombosed access, first occurrence to access thrombosis.
5. Maturation: Vein diameter $\geq 5\text{mm}$ and blood outflow ≥ 500 (-50) mL/min by Doppler ultrasound or fistula is used for dialysis.
Proportion of patients (rate) with mature fistulas can be calculated at defined time points.

Document title: VasQ FDA pivotal Protocol	Document No. CD0121	Revision 12.0 14 March 2021	Page 16 of 42
--	------------------------	-----------------------------------	------------------

6. Time to fistula maturation (physiological): the time (in days) between the fistula placement to date of the earliest confirmation of Vein diameter $\geq 5\text{mm}$ and flow volume in either artery or vein (at least one of them) ≥ 500 (-50) mL/min
7. Time to 100% Functional Fistula Dependency (applicable to patients who enter the study on dialysis): The time (in days) between the fistula placement to the start date of the first 4-week period in which the fistula was the only access available for administration of dialysis.
8. Fistula used for hemodialysis: Proportion of patients (rate) dialyzed through the study fistula. The rate can be calculated at defined time points.
9. Duration between fistula first use for dialysis and final abandonment: The time interval (in days) between first study fistula use for dialysis and the last confirmed use. [REDACTED]
10. Steal³ – Moderate or severe limb ischemia when graded as follows:
 1. Mild - Cool extremity with few symptoms but demonstrable by flow augmentation with fistula occlusion), no treatment needed
 2. Moderate - Moderate (intermittent ischemia only during dialysis/ Claudication), intervention sometimes needed
 3. Severe - Severe (ischemic pain at rest/tissue loss), intervention mandatory
11. Arteriovenous fistula aneurysm – Local outflow vein dilation to at least three times the diameter of the adjacent normal vein with a minimum aneurysm diameter of 2 cm.⁴
12. Access site infection – Infection at anastomosis site graded as follows:
 1. Resolved with antibiotic treatment
 2. Loss of AV access because of ligation, removal, and possible bypass
 3. Loss of limb
13. Seroma³ – Collection of seroma fluid or hematoma at anastomosis site which requires treatment, graded as follows:
 1. Observed, resolved without treatment
 2. Aspirated, surgical treatment
 3. Loss of AV access
14. Device related SAEs or device integrity failures – any identified device failure and/or SAE which is judge by the investigator to be related to the device, as defined in section 8.2.5.

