STUDY DESIGN	
Structure
 
Main study cohort: Prospective, multi-center, single-arm, open label, enrolling a total of 129 patients referred to surgical creation of new brachiocephalic fistula (BCF). The VasQ will be applied to the AV fistula in all patients. The primary effectiveness endpoint for this trial will be measured at 6 months and compared to a performance goal (PG). Safety will compare descriptively between AE rates for Steal, Infection, Aneurysm and Seroma. Patients will be followed up for an additional 18 months for a total of 2 years. Additionally, this trial has several secondary endpoints.
 
Supplementary study cohort: A total of 15 patients will be prospectively enrolled which are referred to surgical creation of a new forearm arteriovenous fistula. VasQ will be applied to the AV fistula in all patients. Patients will be followed in the same manner as in the Main study cohort, however, the data will be reported separately and also included in the secondary [REDACTED] analysis.
 
Duration
 
Primary endpoint is defined at 6 month post index procedure of fistula placement. Patients will be further followed up to 2 years post index procedure.
 
Visit schedule
 
Screening – per eligibility criteria.
 
Index fistula procedure – VasQ implantation.
 
1, 3 months - Doppler US; Clinical examination, SAE follow up; Dialysis status; Access interventions.
 
6 months – Primary endpoint, Doppler US; Clinical examination, SAE follow up; Dialysis status; Access interventions.
 
9 months – Phone call; SAE follow up; Dialysis status.
 
12 months – Doppler US; clinical examination; X-ray imaging of the arm; SAE follow up; Dialysis status; Access interventions.
 
24 months - Doppler US; clinical examination; X-ray imaging of the arm; SAE follow up; Dialysis status

Document title:
VasQ FDA pivotal Protocol

Document No.
CD0121

Revision
12.0
14 March 2021

Page
6 of 42

ENDPOINTS

Primary effectiveness endpoint:

Primary patency rate at 6 months post AVF creation

1 = Success = Intervention free access patency and flow ≥ 500 ml/min determined by Doppler ultrasound.

0 = Failure = Access occluded or flow < 500 ml/min determined by Doppler ultrasound.

The success rate on this primary endpoint will be compared to a PG of 55.0%.

Secondary [REDACTED] analysis:

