6 ENDPOINTS

6.1 Primary effectiveness endpoint

The primary effectiveness endpoint is primary patency at 6 months post AVF creation. Fistulas are defined as primarily patent¹ if they are free from any intervention up to 180 days (endovascular or surgical) to maintain or restore blood flow and demonstrate minimum flow on Doppler or palpable thrill and audible bruit or are receiving dialysis through the fistula.

- The flow criterion is adapted to a range consistent with a documented² interobserver and intraobserver variability, with various ultrasound systems.
- Due to the COVID-19 pandemic, patients are more prone to miss their on-site doppler examination at 6 months, but still undergo access site assessment (i.e. thrill palpation and bruit evaluations) which is a valid assessment for confirmation of patency (Shenoy et al.). Thus, patients that have bruit and thrill data indicating patency or actively receiving dialysis through the fistula at 6 months without interventions, will be considered as success.

1 = Success = Intervention free access patency at 180 days. Confirmation of fistula patency is established by meeting one of the following three conditions:

1. Artery or vein flow ≥ 500 (-50) ml/min determined by Doppler ultrasound.
or
2. Clinical assessment of palpable Thrill and audible bruit at 6 months
or
3. Patient is receiving dialysis through the fistula at 6 months

Note: if patient is not receiving dialysis through the fistula at 6 months, this will not indicate failure.

0 = Failure = Access underwent intervention before 180 days
or

¹ Shenoy, Surendra, et al. "Clinical trial end points for hemodialysis vascular access: background, rationale, and definitions." Clinical Journal of the American Society of Nephrology 13.3 (2018): 490-494.

² Hoyt Kenneth et al. Accuracy of Volumetric Flow Rate Measurements. An In Vitro Study Using Modern Ultrasound Scanners. J Ultrasound Med 2009; 28:1511–1518

Document title: VasQ FDA pivotal Protocol	Document No. CD0121	Revision 12.0 14 March 2021	Page 14 of 42
--	------------------------	-----------------------------------	------------------

None of the following conditions are met at 180 days:

- Flow \geq 500 (-50) ml/min
- Thrill is palpable and bruit is audible
- Patient is receiving dialysis through the fistula

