10.5.2 Full analysis set: Primary Effectiveness Analysis

The full analysis set for the primary effectiveness analysis (FAS_primary) will, consistent with ICH Guideline E9, include all subjects (with brachiocephalic fistulas) for whom the study device was implanted and for whom there is at least one post-procedure Primary Patency measurement.

Handling of missing data: Patients occluded prior to 6 months will be scored as failures even if missing subsequent observations. Patients with missing primary patency at 6 months, but with observed primary patency at later visits (without undergoing interventions) will be considered Success.

Because MI assumes missing at random (MAR), we will conduct sensitivity analyses to assess the sensitivity of our results to alternative assumptions of missingness (see below).

Subjects who died or underwent transplant before 6 months, and were non-occluded at that time of the event, will be excluded from the FAS and reported separately. If such subjects were occluded at or before the time of the event (death or transplant), they will be considered failures and included in FAS for the purpose of the primary analysis.

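### The failure rule in 6.1 omits thrombosis or occlusion before day 180, so a fistula that occludes early and is open at 6 months without intervention is scored differently by 6.1, 6.4 and 10.5.2

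*Combined protocol and SAP*

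**What the plan says.** Four places in the combined protocol and SAP bear on the scoring of primary patency.

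- **Section 6.1, success.** The subject must be free of intervention. "Confirmation of fistula patency is established by meeting one of the following three conditions": sufficient Doppler flow, thrill with bruit, or dialysis through the fistula. These are alternatives, so a Doppler reading is not required.
- **Section 6.1, failure.** There are two limbs. The first is "Access underwent intervention before 180 days". The second is "None of the following conditions are met at 180 days", followed by the same three conditions. Neither limb names thrombosis or occlusion, and the second looks only at status at day 180.
- **Section 6.4 no. 1.** Primary patency runs until the first intervention "or first occurrence to access thrombosis". The section adds that a rate can be computed at set time points. Several lines of this item are redacted.
- **Section 10.5.2, under the missing-data heading.** "Patients occluded prior to 6 months will be scored as failures even if missing subsequent observations". The next sentence reads: "Patients with missing primary patency at 6 months, but with observed primary patency at later visits (without undergoing interventions) will be considered Success". It makes no exception for an earlier occlusion.

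The synopsis does name occlusion in its failure rule ("0 = Failure = Access occluded or flow"), but does not say whether it means occlusion at any time or only at 6 months.

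**The concern.** The primary endpoint is called primary patency, yet the rule that scores it in 6.1 drops one of the two events that end primary patency in 6.4. A subject who has lost primary patency by the protocol's own definition can be counted as a primary success. The same subject would have an event before day 180 in secondary endpoint 1 (time to loss of primary patency), so the two results would disagree about one person.

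Section 6.2.1 adds to this. It leaves thrombosis out of the four main safety endpoints because the effectiveness endpoints are said to cover it. Under 6.1 the primary endpoint covers thrombosis only if it led to an intervention or if no patency condition is met at day 180.

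The test is a count against a fixed threshold. An unsettled scoring rule leaves a choice to be made after the data are seen, and near the threshold one subject decides the result.

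**Working it through.** **1. Score the possible courses under each rule.** Take a fistula documented as occluded at month 3.

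| What follows | 6.1 | 6.4 no. 1 | 10.5.2 |
|---|---|---|---|
| A. Reopened by a recorded intervention before day 180 | Failure | Patency ended | Failure |
| B. Still occluded, no condition met at day 180 | Failure | Patency ended | Failure |
| C. No intervention; flow, thrill and bruit, or dialysis use at 6 months | **Success** | Patency ended | Failure, unless confined to missing 6-month data |
| D. No intervention; month 6 missing; patent at month 12 | No 6-month assessment to score | Patency ended | **Failure by one sentence, Success by the next** |

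Only C and D conflict. In C, 6.1 conflicts with 6.4 however 10.5.2 is read. In D, the conflict lies within 10.5.2 itself.

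**2. Reproduce the plan's figures.** Inputs from sections 10.4 and 10.6.3: performance goal 55%, assumed rate 70%, 116 evaluable, two-sided exact 95% interval, about 10% dropout.

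- Lower limit for x successes in n: the 0.025 quantile of Beta(x, n − x + 1).
- 75/116 = 64.7%, lower limit 55.2%: passes. 74/116 = 63.8%, lower limit 54.4%: fails. The pass mark is 75.
- Power: P(X ≥ 75 | n = 116, p = 0.70) = 0.911, against the stated 90%.
- Enrolment: 116 / 0.90 = 128.9, rounded up to 129, as stated.

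The sample size reproduces and does not depend on this wording.

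**3. Illustrate the effect on the test.** The documents give no frequency for C or D. Assume that the rate under the 6.4 definition is exactly 55%, and that 6.1 adds k successes per 116 subjects on average. The chance of passing is P(X ≥ 75 | n = 116, p = 0.55 + k/116).

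| k (assumed) | p | Chance of passing |
|---|---|---|
| 0 | 0.5500 | 2.2% |
| 1 | 0.5586 | 3.4% |
| 2 | 0.5672 | 5.1% |
| 3 | 0.5759 | 7.3% |

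The nominal one-sided level is 2.5%, so one such subject on average is enough to exceed it.

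**The case against.** The strongest reply is that the sections, read together, already point to failure. Section 6.1 names its endpoint primary patency, 6.4 defines that term as ending at thrombosis, and 10.5.2 and the synopsis both mention occlusion. On this view the three conditions in 6.1 only confirm patency and do not replace the definition. That is a reasonable reading, but 6.1 sets out its own complete success and failure rule, and no visible text subordinates it. The 10.5.2 sentence stands under a missing-data heading, so it may not reach a subject with a 6-month assessment.

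The redacted lines under 6.4 no. 1 may deal with the case. This limits the claim to the visible text.

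A reader might infer three stronger things, none of which the documents support:

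- *That any fistula occluded early and later open is affected.* One reopened by a recorded intervention before day 180 fails under every rule, as does one that meets no patency condition at day 180.
- *That rescues at other centres go unrecorded and pass as successes.* Nothing in the documents describes this. Interventions are documented at months 1, 3 and 6, and section 12 sends failures and interventions to committee review. An uncaptured intervention would in any case be a data problem, not a fault of the definition.
- *That the error always favours the device.* If the early occlusion reading was itself wrong, success under 6.1 is the right score.

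It is also fair that one subject changes the result only at exactly 75/116. At the planned 70% rate the chance of landing there is P(X = 75 | n = 116, p = 0.70) = 3.6%. Secondary endpoint 1 is exploratory.

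**Conclusion.** The scoring rule of the primary endpoint is wrong as written, with low severity. For a fistula with documented thrombosis or occlusion before day 180, no recorded intervention, and a patency condition met at 6 months, 6.1 gives success while 6.4 no. 1 says primary patency has ended. Section 10.5.2 gives failure if it is not confined to missing 6-month data. Where month 6 is missing and the fistula is patent later without intervention, 10.5.2 gives both scores.

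The contradiction rests on the visible wording alone. Its numerical effect rests on assumed counts: the rise from 2.2% to between 3.4% and 7.3% is an illustration for 1 to 3 subjects, not an estimate. The affected group is probably small.

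**What to change.** Add a third limb to the failure rule in 6.1, for example: *or access thrombosis/occlusion before 180 days, confirmed by the core lab or the clinical events committee, whether or not flow later returns*. The confirmation condition keeps a misread early scan from becoming a failure.

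In 10.5.2, make the sentence that grants success on later patency subject to there being no earlier confirmed occlusion. Align the synopsis, so that 6.1, 6.4 no. 1, 10.5.2 and the synopsis score the subject the same way.

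The cost is a few clauses. Patency is already assessed at months 1 and 3, images already go to the core lab, and the committee already reviews fistula failures, so no new visits or data are needed. The primary rate may become slightly less favourable. If the planned 70% was meant on the 6.1 rule and one subject in 116 is rescored, power is P(X ≥ 75 | n = 116, p = 0.70 − 1/116) = 0.873, against 0.911.

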6.2 Safety endpoints

6.2.1 Main safety endpoints

The main secondary endpoints in this trial are, for each subject, occurrence of the following clinically meaningful safety events at up to 6 months:

- Steal
- Infection
- Aneurysm
- Seroma

These four safety endpoints have been selected since they are the major non-thrombotic access site complications associated with fistulas. Thrombotic complications which affect maturation and patency will be covered in this trial by the primary and secondary effectiveness endpoints.

These endpoints, which are defined in Section 6.4, will be scored dichotomously for each subject as 0 (did not occur) or 1 (occurred); i.e. each subject is scored 0 or 1 on each of the four endpoints. Additionally, the cumulative number of events over all subjects will be computed. This will allow both detailed and general comparisons to the relevant literature.

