10.6.6 Secondary endpoints

Secondary endpoints will be considered exploratory and will be presented descriptively, along with associated 95% confidence intervals. The analysis sets for each endpoint are as follows:

1. Time to primary patency cessation since the fistula creation - *FAS primary and FAS secondary analysis sets*
2. Time to assisted primary patency cessation since the creation - *FAS primary and FAS secondary analysis sets*
3. Time to primary patency cessation since the first intervention (post-intervention primary patency) - *FAS primary and FAS secondary analysis sets*
4. Time to assisted primary patency cessation since the first intervention (post -intervention assisted primary patency) - *FAS primary and FAS secondary analysis sets*
5. Time to first successful cannulation – *Ongoing dialysis subset*
6. Time to secondary patency cessation since the fistula creation - *FAS primary and FAS secondary analysis sets*
7. Time to secondary patency cessation since the first intervention (post intervention secondary patency) - *FAS primary and FAS secondary analysis sets*
8. Time to fistula maturation (physiological) - *FAS primary and FAS secondary analysis sets*
9. Time to 100% functional fistula dependency – *Ongoing dialysis subset*
10. Unassisted maturation at 3 months defined as vein diameter \geq 5mm and blood outflow \geq 500 (-50) mL/min by Doppler ultrasound - *FAS primary and FAS secondary analysis sets.*

Document title: VasQ FDA pivotal Protocol	Document No. CD0121	Revision 12.0 14 March 2021	Page 39 of 42
--	------------------------	-----------------------------------	------------------

11. Primary patency at 6 months post AVF creation, excluding patients who have received balloon angioplasty procedures directed at cephalic arch and central vein stenosis *FAS primary and FAS secondary analysis sets*.
12. Time to first intervention - *FAS primary and FAS secondary analysis sets*
13. Number of interventions (including type and outcome) - *FAS primary and FAS secondary analysis sets*
14. Rate of interventions per patient-years - *FAS primary and FAS secondary analysis sets*
15. Primary Failure, at 6 months, which is fistula permanent failure before hemodialysis suitability - *FAS primary and FAS secondary analysis sets*
16. Target artery / target vein flow (mL/min) at 1, 3 and 6 months by Doppler blood outflow measurement - *FAS primary and FAS secondary analysis sets*

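### As defined in 6.4 no. 4, assisted primary patency has no end event for a fistula ligated, removed or abandoned without thrombosis, so secondary endpoints 2 and 4 are overstated

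*Combined protocol and SAP*

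**What the plan says.** Section 6.4 defines three patency times.

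- **Primary patency (no. 1)** runs "until any first intervention (endovascular or surgical) to maintain or restore blood flow, or first occurrence to access thrombosis". Redacted lines follow directly within this item.
- **Secondary patency (no. 2)** is "the time of access creation or placement until access abandonment, and includes all surgical and endovascular interventions".
- **Assisted primary patency (no. 4)** runs "until any first intervention (endovascular or surgical) to restore blood flow of a thrombosed access, first occurrence to access thrombosis". Nothing in this item is redacted.

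Section 6.3 uses the assisted definition in endpoint 2, "Time to assisted primary patency cessation since the creation", and in endpoint 4, the same time counted from the first intervention.

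The protocol expects accesses to be lost in other ways. Infection grade 2 (6.4 no. 12) is "Loss of AV access because of ligation, removal, and possible bypass", and seroma grade 3 (6.4 no. 13) is also loss of the access. Section 6.2.1 says of steal, infection, aneurysm and seroma: "These four safety endpoints have been selected since they are the major non-thrombotic access site complications associated with fistulas".

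Section 10.6.6 assigns analysis sets to the time-to-event endpoints. It gives no visible rule for abandonment, ligation or removal, and no censoring rule.

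**The concern.** Assisted primary patency is the stricter of the two measures: it should end no later than secondary patency in the same subject. With the end events as listed, that order can fail. A fistula taken down for infection has not thrombosed, and ligation does not restore flow to a thrombosed access, so neither event in no. 4 occurs. The same holds for a low-flow fistula given up for another access while still open.

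The omission works in one direction only. It leaves accesses lost through infection, seroma or non-maturation out of the events and so favours the device. It also leaves two analysts free to treat the same subject differently, because no visible text says whether such a subject is still at risk or censored at the loss. An assisted curve lying above the secondary curve would be hard to explain in a report.

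**Working it through.** The plan states no figure for this point, so there is none to reproduce. The check is a comparison of end events, followed by an illustration with assumed counts.

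**Step 1. End events by type of loss (6.4 nos. 2 and 4).**

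| What happens to the access | Assisted primary (no. 4) | Secondary (no. 2) |
|---|---|---|
| Thromboses and is abandoned | Ends at thrombosis | Ends at abandonment |
| Thromboses and is salvaged | Ends at thrombosis | Continues |
| Ligated, removed or abandoned, never thrombosed | No event | Ends at abandonment |

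The third row is the gap. One such subject is enough to break the per-subject order if carried as patent. If censored at the loss instead, the subject has an event for secondary patency and none for assisted patency.

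**Step 2. Cohort rates in simple counts.** Let N be the subjects, T those thrombosed and abandoned, S those thrombosed and salvaged, and L those lost without thrombosis.

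- Assisted as written, losses carried as patent: (N − T − S)/N
- Assisted with loss as an event: (N − T − S − L)/N
- Secondary: (N − T − L)/N

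Assisted as written exceeds secondary when N − T − S > N − T − L, that is, when L > S. With loss counted as an event, assisted cannot exceed secondary for any L.

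**Step 3. Numbers.** N = 129 is the main cohort (section 10.4). T, S and L are assumed, because the documents give none of them.

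| T | S | L | Assisted as written | Assisted with loss as event | Secondary | Reversed? |
|---|---|---|---|---|---|---|
| 12 | 0 | 1 | 117/129 = 90.7% | 89.9% | 116/129 = 89.9% | Yes |
| 12 | 0 | 3 | 90.7% | 88.4% | 114/129 = 88.4% | Yes |
| 12 | 0 | 10 | 90.7% | 82.9% | 107/129 = 82.9% | Yes |
| 12 | 4 | 3 | 113/129 = 87.6% | 85.3% | 88.4% | No |
| 12 | 4 | 6 | 87.6% | 82.9% | 111/129 = 86.0% | Yes |

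The overstatement is L/N in every row, whether or not the rates reverse: 3/129 = 2.3 points for three losses and 10/129 = 7.8 points for ten.

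**Step 4. Censoring at the loss.** With T = 12, S = 0, thromboses assumed every 15 days to day 180 and losses assumed every 5 days from day 60, the Kaplan-Meier assisted estimate is 90.5% against 88.4% for secondary at L = 3. At L = 10 it is 90.2% against 82.9%. Censoring therefore does not remove the overstatement.

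**The case against.** The strongest defence is that the design is deliberate. Section 6.2.1 assigns non-thrombotic complications to safety and thrombotic ones to effectiveness, so an assisted patency based on thrombosis fits that division. The losses are also visible elsewhere: in secondary patency (endpoints 6 and 7), primary failure (15), use for dialysis (19), time to abandonment (20), and the infection and seroma grades tabulated under 10.6.5. Section 12 sends all fistula failures to the committee. Finally, 10.6.6 states: "Secondary endpoints will be considered exploratory and will be presented descriptively, along with associated 95% confidence intervals". No success decision depends on endpoints 2 and 4.

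Most of this stands, and it limits the importance of the point. It does not repair the definition. Reporting a loss under another endpoint does not justify counting the same access as patent, or censoring it as if the loss were unrelated to patency.

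Three stronger readings are tempting, and the documents do not support them.

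- **That primary patency (endpoints 1 and 3) has the same fault.** The visible sentence of no. 1 does omit abandonment, but the redacted lines after it may supply it. This cannot be verified.
- **That the 6-month primary test is biased.** Section 6.1 scores failure when "None of the following conditions are met at 180 days", the conditions being adequate flow, thrill with bruit, or dialysis through the fistula. A ligated or removed fistula meets none of them. A fistula given up while it still has a thrill and bruit could score as a success, but that follows from 6.1 itself and not from 6.4 no. 4.
- **That the effect can be sized from Table 10-1.** Adding infection (7.5%) and steal (5.1%) double-counts, because 10.2.1 says the rates overlap. Those data run to about 6 months, not 24. The share of such events that costs the access is not given anywhere.

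**Conclusion.** The point holds for assisted primary patency, that is, secondary endpoints 2 and 4. As written, a fistula lost without thrombosis has no event there. Whether carried as patent or censored, it raises the estimate. If carried as patent, it also lets a subject's assisted time exceed the secondary time.

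A reader might infer that the assisted curve must end up above the secondary curve. It need not: in simple counts this happens only when losses without thrombosis outnumber salvaged thromboses.

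The definitional gap rests on unredacted text and needs no assumption. The size cannot be derived from the documents, and the percentages above are illustrations with assumed counts. The consequence is confined to the interpretation of exploratory, descriptive endpoints. The primary test against 55% is essentially unaffected.

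**What to change.** 1. In 6.4 no. 4, add as a further end event: or access abandonment, ligation or removal, whichever occurs first. Code that date as an event in endpoints 2 and 4.
2. Do not extend this to every reason for giving up a fistula. Censor subjects whose non-occluded fistula is given up because of transplant, or who die with a non-occluded fistula. This is consistent with 10.5.2, which does not count such subjects as failures and already excludes those before 6 months from the analysis set. The censoring rule is mainly needed after that.
3. Apply the same event and censoring rule to secondary patency (endpoints 6 and 7), and state it in 10.6.6.
4. Confirm that the redacted text of no. 1 treats abandonment, ligation and removal in the same way for primary patency, and add it if it does not.
5. Program a per-subject check that assisted primary patency time does not exceed secondary patency time, and that no subject with a secondary patency event is censored for assisted patency.

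The cost is one phrase, a short censoring rule and a programming check. Abandonment dates are already needed for secondary patency, so no new data are collected. The downside for the sponsor is a slightly less favourable assisted patency curve.
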